The HPV 9-10 Trial: Early Initiation of HPV Vaccination
PI: [name] MPH and [name] MPH
NCT #: NCT04722822
Statistical Analysis Plan
Based on original for NIH grant submission July 2019
Date created for CT.gov: September 3, 2025

Aim 2: Conduct a cluster-randomized pragmatic trial comparing HPV9-10yrs vs HPV11-12yrs and, using the RE-AIM framework, assess the following effectiveness outcomes:

a. Primary outcome: Age at HPV series completion

Hyp 2a: Patients in HPV9-10 practices will have earlier age at vaccine completion than those in HPV11-12.

b. Secondary outcome: HPV completion by age 13

Hyp 2b: Patients in HPV9-10 practices will have higher proportions completing HPV series by age 13 than those in HPV11-12.

c. Secondary outcome: Age at HPV series initiation

[figure not shown]
Hyp 2c: Patients in HPV9-10 practices will have earlier age at vaccine initiation (i.e., age at first dose) than those in HPV11-12.

Overall Strategy: Descriptive statistics will be computed for patient and practice characteristics, initially reporting on differences between: (1) different treatment arms and (2) patient dropouts vs. non-dropouts. Covariates to be adjusted for in multivariable models at the patient level include age, gender, and type of insurance. The primary analysis will employ the intent-to-treat principle. We will follow patients prospectively for 4 years, assessing series completion status for each patient at the end of follow-up; patients not seen by the practice at follow-up will be assumed not to have completed vaccination by end of study and will be treated as censored. We will explore, using interaction effects in regression models, whether practice type, payer mix (mostly commercial or Medicaid), patient socio-demographics, and number of providers in a practice impacts intervention effectiveness. Goodness-of-fit statistics and model fitting diagnostics will be used to assess for influential points, outliers and to evaluate alternative model specifications. Hypothesis tests will be two-sided with $\alpha = 0.05$ and p-values will be reported. We will follow recent guidelines for statistical analysis plans of randomized trials and the CONSORT statement to report cluster-randomized trials. All statistical analyses will be performed using R or SAS version 9.4 (SAS Institute Inc., Cary, N.C.).

a. **Primary Outcome: Age at HPV series completion**

To test the primary study hypothesis that eligible patients ages 9-10 in the HPV9-10 practices will have earlier HPV series completion rates relative to those in HPV11-12 practices, we will use a Cox proportional hazards regression model to compare age at vaccination between study arms. Patients not experiencing the event of interest will be administratively censored at end of study. The model will include a practice-level treatment group indicator, along with covariates as listed above. Comparison between groups will be performed by testing whether the hazard ratio between the 11-12 arm and the 9-10 arm is different from 1; clustering of patients within practices will be accounted for using robust covariance estimators. We estimated power based on the log-rank test for equality of survival curves using Monte Carlo simulations in R based on 1000 datasets.

Because there will likely be few or no individuals completing vaccination by age 11 in the control arm, we have assumed that the hazard in the control arm is 0 between 9 and 11 years of age, and that the hazard in the treatment arm starts to increase from age 9. Assuming an intraclass correlation coefficient (ICC) within practices of 0.01 and 14 practices per treatment arm with 100 patients per practice, with 3.5 years of follow-up we will have 85.5% power ($\alpha=0.05$) to detect a 6.0-month difference in median age at completion between treatment arms (corresponding to a difference in proportion completing by age 13 of 6%). Even with a 50% reduction in our effective sample size (ESS), we will have 83.0% power to detect an 8.2-month difference in medians between treatment arms. Holding all else constant, this reduction in ESS is consistent with (a) an ICC of 0.03; (b) 7 practices per arm (c) 34 patients per practice (see Figure).

Difference in median age at completion (months)

b. **Secondary Outcome: proportion completing HPV series by age 13**

To estimate proportion completing the HPV series by age 13, estimates of the survival curve for age at HPV series completion will be computed for each treatment arm based on the Cox regression models fitted for the primary analysis, using the estimated baseline hazard function; the statistic of interest is the difference between these estimates at age 13. We use survival analysis methods here (rather than logistic regression) because the analysis needs take into account that patients may be followed for different lengths of time, and they may or may not experience the event of interest by the end of the study. Standard errors will be estimated using the cluster bootstrap: resampling will occur at the practice level. Using the same simulations as described above to estimate power for the primary outcome, we found that the study will have 86.4% power to detect a 9% difference in the proportion completing by age 13 between treatment arms. This effect size corresponds to a completion rate at age 13 of 30% among controls and 39% among treated subjects.

c. **Secondary Outcome: Age at HPV series initiation**

The methods for estimating differences between treatment arms for the secondary outcome of age at HPV series initiation will be identical to those for the primary outcome (age at completion). The event of interest is series initiation (i.e., age at first dose). To estimate power, we used the same simulation design described above, now basing control initiation survival curves on previous data suggesting an initiation rate of 50% at age 13. The simulation results indicate that we will have >90% power ($\alpha=0.05$) to detect an effect size equivalent to a difference in median age at initiation of 4.4 months. With a 50% reduction in ESS, we will still have 80.6% power to detect a difference in median age at initiation of 5.2 months.

Subgroup analyses

Sex as a biological variable: Although HPV vaccination is effective in both genders, HPV infection presents differently and causes different types of cancers in males and females. The vaccine was also recommended later for males, which may also affect rates of uptake by sex. Therefore, it is important to assess outcomes by gender.

HPV vaccine completion and initiation by gender, insurance and state

As for the primary outcome, Cox regression with standard errors adjusted for correlation within practices will be used to evaluate differences in treatment effect on age at vaccine initiation and completion within specified subgroups. The statistical analysis will involve tests of interaction terms between treatment and subgroup variable (e.g. gender) in the regression model. We do not expect to have data on ethnicity and race from all practices, therefore we will only be able to examine racial or ethnic differences in a subset of our practices.

Receipt of other adolescent vaccines (Tdap, MenACWY)

As for the primary outcome, Cox regression with standard errors adjusted for correlation within practices will be used to evaluate whether the intervention has any effect on receipt of other vaccines. The outcome will be age at completion of other vaccine (series), and patients not receiving these vaccines by end of study will be treated as censored. The statistical analysis will involve tests of the indicator for treatment status of the practice.

Other considerations

There are other potential methodological complexities in the analysis of the outcomes of this study, including left truncation and non-proportional hazards. Left truncation. We do not anticipate that left truncation will be a major issue for our primary study outcome because we only intend to include patients aged 9-10 at baseline, and vaccination rates in this age group should be zero. However, this could be an issue for some secondary outcomes, such as age at receipt of other childhood vaccines. Therefore, age of the child at baseline will be accounted for using delayed entry, as failure to account for this issue could lead to biased inference. Non-proportional hazards. We will test the proportional hazards assumption to see if any deviation is statistically significant; if found to be violated, we will employ alternative modeling strategies (e.g., time-dependent covariates/interactions, additive hazards regression). We note that even if there is evidence of non-proportional

hazards, the log-rank test remains valid, so we have chosen to use this for our power calculations. We will also perform a sensitivity analysis using Kaplan-Meier curves to assess the validity of some of the assumptions made by the Cox model, including proportional hazards. The Cox model essentially compares treatment arms across the entirety of the survival curve, while comparison of Kaplan-Meier curves at age 13 allows us to obtain more direct estimates of the treatment's effect on this particular endpoint. Losses to follow-up. Because it is possible that patients will be lost to follow-up prior to the administrative censoring we will apply at the end of the study, we will employ sensitivity analyses to determine how different assumptions regarding losses to follow-up might affect our results.

Outcome	Type	Number of subjects	Effect size	Power	Method
age at HPV series completion	Primary	2800	6.0-month difference in median ages	86%	Cox regression with robust covariance estimator
HPV completion by age 13 years	Secondary	2800	9%	86%	KM estimates with cluster bootstrap for variance estimation
age at HPV series initiation	Secondary	2800	4.4-month difference in median ages	>90%	Cox regression with robust covariance estimator

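### The plan's own hazard assumption rules out proportional hazards, so the primary test should be fixed regardless of the proportional-hazards check and the age-13 proportions taken from Kaplan-Meier

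*SAP*

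**What the plan says.** Under the primary outcome, the arms are compared with a Cox model on the age scale by "testing whether the hazard ratio between the 11-12 arm and the 9-10 arm is different from 1", with a robust variance for clustering by practice. The power paragraph that follows says of controls: "we have assumed that the hazard in the control arm is 0 between 9 and 11 years of age". The 9-10 practices are treated differently over those same two years, because there "the hazard in the treatment arm starts to increase from age 9". Power is quoted from log-rank simulations: "with 3.5 years of follow-up we will have 85.5% power". The effect is a 6.0-month difference in medians, said to correspond to 6 percentage points at age 13. Overall Strategy gives a different duration: "We will follow patients prospectively for 4 years".

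Under Other considerations, proportional hazards will be tested for significance. If they are found violated, alternative models will be used, with time-dependent terms and additive hazards given as examples. The same section says that the log-rank test stays valid without proportional hazards and adds Kaplan-Meier curves as a sensitivity analysis. It also says that baseline age will be handled by delayed entry.

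For the secondary outcome at age 13, the text takes each arm's proportion from survival curves "based on the Cox regression models fitted for the primary analysis, using the estimated baseline hazard function". The closing summary table instead lists Kaplan-Meier estimates with a cluster bootstrap for that outcome.

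**The concern.** A control hazard of zero against a positive treated hazard before 11, followed by positive hazards in both arms, cannot be one finite constant ratio. Three things follow.

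- **Meaning of the hazard ratio.** It averages over whatever ages are observed. The SAP gives entry only as ages 9-10 and gives two follow-up lengths, so the same true effect can produce different reported ratios.
- **Pre-specification.** The plan foresees the violation but answers it with a significance test and an open list. It does not fix the test statistic, the model, any split of the age axis, or whether the replacement takes over the primary test. The listed models need not agree.
- **The age-13 proportions.** Read from a proportional-hazards fit, they inherit the misfit, and the SAP names two methods for this one outcome.

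**Working it through.** **Inputs.** From the SAP: control hazard 0 from 9 to 11; treated hazard positive from 9; 30% of controls complete by 13 (secondary outcome b); a 6-point and 6.0-month effect; 14 practices of 100 per arm; ICC 0.01; follow-up 3.5 or 4 years. Assumed, because the SAP does not state them: the 30% also applies to the 6-point effect; the control hazard after 11 is Weibull with shape s; entry is at 9.0, uniform 9-10 or uniform 9-11; the early treated hazard is constant or ramped.

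**1. The SAP's effect pair.** Let the control cumulative hazard be H0(t) = 0.357 × ((t−11)/2)^s after 11, since −ln 0.70 = 0.357. Let the treated arm accumulate e between 9 and 11, then k × H0.
- At 13: e + 0.357k = −ln 0.64 = 0.446.
- At the treated median, 6.0 months before the control median: e + k × H0 = ln 2 = 0.693.
- Flat (s = 1): control median 11 + 0.693/0.178 = 14.89; e = 0.090, k = 1.00. So 1 − exp(−0.090) = 8.6% of treated children complete before 11 and the hazards are equal afterwards.
- Rising (s = 1.3): control median 14.33; e = 0.016 (1.6% before 11), k = 1.21.
- At s = 1.35, e is about 0 and k = 1.25.

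As a check, with s = 1 and k set to exactly 1, e = 0.446 − 0.357 = 0.0896 (unrounded) and the medians differ by 0.0896/0.178 = 0.50 years, or 6.03 months. This matches the SAP. A constant ratio of 0.446/0.357 = 1.25 on the same control curve would shift the median by 9.4 months (14.89 to 14.11). The pair therefore fits an early effect well, but does not prove which hazards were simulated.

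**2. What the Cox model estimates.** Let Yj(t) be the share of arm j at risk at age t (entered, still followed, not completed) and dNj(t) its completions. In large samples the log hazard ratio b solves Σ[dN1 − p(dN0 + dN1)] = 0, with p = Y1·e^b/(Y1·e^b + Y0). The Cox-predicted completion at 13 uses Λ = Σ(dN0 + dN1)/(Y0 + Y1·e^b) up to 13: 1 − exp(−Λ) for controls and 1 − exp(−Λ·e^b) for the 9-10 arm. Ratios are 9-10 v 11-12, without covariates or practice effects; ranges span the two early-hazard forms. The true difference at 13 is 6.0 points throughout.

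| Entry | Follow-up (years) | HR, flat | Age-13 difference, flat | HR, s = 1.3 | Age-13 difference, s = 1.3 |
|---|---|---|---|---|---|
| 9.0 | 3.5 | 1.39 | 13 not reached | 1.28 | 13 not reached |
| 9.0 | 4 | 1.31 | 7.1 | 1.26 | 6.2 |
| 9-10 | 3.5 | 1.23-1.28 | 5.5-6.6 | 1.25-1.26 | 5.9-6.1 |
| 9-10 | 4 | 1.19-1.23 | 4.7-5.6 | 1.24-1.25 | 5.7-5.9 |
| 9-11 | 3.5 | 1.13-1.17 | 3.2-4.2 | 1.23-1.24 | 5.5-5.7 |
| 9-11 | 4 | 1.11-1.15 | 2.8-3.7 | 1.23 | 5.4-5.6 |

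In simulation with a flat hazard, Kaplan-Meier estimates recovered 5.9 to 6.2 points.

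**3. The fallback.** In simulated trials of the planned size (1000 per setting; 600 with no early effect), a treatment-by-age test of proportional hazards was significant in 95-100% with a flat hazard, 14-80% at s = 1.3, and 6-9% with no effect before 11. One reading of the two named alternatives is a 2-df treatment and treatment-by-age test and a constant-effect additive model. On that reading they disagreed on significance in 9-69% of trials (flat) and 15-27% (s = 1.3), against 6-8% with no treatment effect.

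**4. The stated 85.5% power.** This cannot be reproduced, because hazard shapes and entry ages are not given. With a flat control hazard, a ramped early hazard, 3.5 years and 400 runs, robust Cox power was 90% with entry at 9.0 and 41% with entry uniform over 9-11. The stated figure lies between the two.

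**The case against.** The best defence is that the plan saw the problem. It simulated log-rank power under the non-proportional hazards it assumed, and the log-rank test is in essence the unadjusted Cox score test before the cluster correction. The comparison was therefore powered under this alternative. The zero hazard is a planning simplification, and the effect pair alone would also fit a proportional effect (s = 1.35), although that contradicts the stated treated hazard from age 9. The text on alternatives does not say outright that they displace the primary test. All of this stands, and it limits what can be claimed.

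A reader might infer more than the document supports:

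- **That the primary test is invalid or points the wrong way.** With no treatment effect the hazards are equal and so proportional. Simulated null rejection for robust Cox was 5.8-7.6% (9.5% in one 400-run check); non-proportional hazards cannot cause that excess.
- **That the check will almost surely fail.** This depends on the control hazard after 11, which is not stated.
- **That the trial is underpowered.** The low power figures need wide entry ages and a particular hazard shape.
- **That a restricted mean must become primary.** Capped at 12.5 or 13, it stops below both medians used for power. With the effect only after 11, its power was 48-58% against 58-75% for Cox.

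The defence does not answer two points: the status of the fallback is open, and the age-13 outcome has two methods.

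**Conclusion.** The concern holds for interpretation and pre-specification, and should be fixed. Under the SAP's own planning hazards the single hazard ratio is not a constant effect: about 1.11-1.39 (flat) or 1.23-1.28 (s = 1.3) for one and the same true effect. The Cox-derived age-13 difference can be about 2.8-7.1 points (flat) or 5.4-6.2 (s = 1.3) against a true 6. The sizes rest on assumed hazard shapes, entry ages and a 30% control rate, and are modest if the control hazard rises after 11. The open fallback and the conflict between the text and the table do not depend on those assumptions. Type I error and direction are not at issue, and the case does not require a new primary estimand.

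**What to change.** 1. State that the primary test remains the pre-specified cluster-robust Cox (log-rank-type) comparison whatever the proportional-hazards test shows. Remove that test as a trigger for changing the primary analysis, and label the time-varying and additive models as sensitivity analyses.
2. For age 13, replace the Cox-based rule with delayed-entry Kaplan-Meier estimates by arm and the practice-level cluster bootstrap, in line with the summary table.
3. Report the Kaplan-Meier curves beside the hazard ratio as the description of effect, and describe the ratio as an average over the observed follow-up.
4. State the hazard shapes, entry ages and one follow-up length behind the 85.5% power. This also bears on item 2: with 3.5 years, only children entering at 9.5 or later (13 − 3.5) can be observed to 13.
5. Optionally add, as supportive, a delayed-entry restricted mean age at completion up to a fixed upper age.

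The cost is SAP wording, a short program and slightly wider intervals for the age-13 difference. If outcome data have already been seen, the change should be dated and labelled as such.

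### The practice-level treatment effect is tested with robust covariance on 28 practices and no small-sample provision; as a standard Wald z test its type I error is about 7%, not 5%

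*SAP*

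**What the plan says.** In the section on the primary outcome, the Cox model carries a treatment indicator defined at practice level, the test is of a hazard ratio of 1, and "clustering of patients within practices will be accounted for using robust covariance estimators". The summary table at the end gives the method as "Cox regression with robust covariance estimator". Under Overall Strategy, the sentence beginning "Hypothesis tests will be two-sided with" sets alpha at 0.05. The power calculation assumes "14 practices per treatment arm with 100 patients per practice", so 28 practices and 2,800 patients.

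The same approach is used elsewhere:
- **Age at initiation** (section c) uses methods identical to the primary outcome.
- **Subgroups and other adolescent vaccines** are each introduced by reference to the primary outcome: "Cox regression with standard errors adjusted for correlation within practices will be used". For other vaccines the inference is by "tests of the indicator for treatment status of the practice".
- **Completion by age 13** (section b) uses a bootstrap: "Standard errors will be estimated using the cluster bootstrap: resampling will occur at the practice level".

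The SAP nowhere gives a finite-cluster correction, degrees of freedom, a t reference or a permutation test, and it does not choose between Wald and score. Section b does not say whether resampling is done within arm, or how the bootstrap standard error is turned into a test or interval.

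**The concern.** Treatment differs only between practices, so the variance of its coefficient is estimated from 14 practice-level contributions per arm, however many patients each contributes. With that few, the uncorrected sandwich has two faults. It is biased low, because the residual contributions are taken around fitted values from the same practices. It is also imprecise, so the Wald ratio has heavier tails than the normal. Both faults raise the type I error.

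The plan's wording allows procedures with clearly different error rates. The one most software produces by default, a Wald z test with clustered standard errors, exceeds the declared 5%. This affects the primary test, the initiation test and the other-vaccine tests, and any 95% intervals reported with them. Leaving the form open also allows it to be chosen after the data are seen.

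**Working it through.** **Inputs from the SAP.** Two-sided alpha 0.05; k = 14 practices per arm; 100 patients per practice; ICC 0.01; 30% of controls complete by age 13; stated power 85.5%.

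**The plan's own figures first.** With design effect 1 + (m − 1) × ICC, the effective sample size per arm is:

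| Scenario | Design effect | ESS per arm | Ratio |
|---|---|---|---|
| Base case | 1.99 | 1400/1.99 = 704 | 1 |
| ICC 0.03 | 3.97 | 1400/3.97 = 353 | 0.501 |
| 7 practices per arm | 1.99 | 700/1.99 = 352 | 0.500 |
| 34 patients per practice | 1.33 | 476/1.33 = 358 | 0.509 |

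The halved-ESS statement therefore reproduces. The 85.5% power cannot be reproduced, because the SAP does not give the hazard shapes. Weibull shapes that satisfy 30% versus 36% by age 13 and a 6-month gap in medians gave anything from 21% to 100%.

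**Closed-form size.** For equal practices, the uncorrected sandwich behaves like a between-practice variance with divisor k instead of k − 1, on 2(k − 1) degrees of freedom.
- 14 per arm: P(|t26| > 1.96 × √(13/14)) = P(|t26| > 1.889) = 7.0%.
- The reference distribution alone, with an unbiased variance: P(|t26| > 1.96) = 6.1%.
- 7 per arm: P(|t12| > 1.96 × √(6/7)) = P(|t12| > 1.815) = 9.5%.
- Interval width at 14 per arm: 1 − 1.96/(2.0555 × √(14/13)) = 8.1% too narrow, so coverage is 93.0%.

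**Simulated size of the Cox test.** There were 10,000 null trials per setting (Monte Carlo SE about 0.25 points), with 14 practices per arm and 100 patients per practice on average. Assumed: 30% complete by age 13; practice log-hazard SD 0.175 or 0.30; for unequal sizes, a coefficient of variation (CV) of 0.6. The Kauermann–Carroll and Mancl–DeRouen rows use practice leverage approximated by the practice's share of its arm's expected events.

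| Test | Equal sizes | CV 0.6 |
|---|---|---|
| Uncorrected sandwich, Wald z | 6.6–7.1% | 8.2–8.6% |
| k/(k − 1) correction, t26 | 4.6–5.1% | 5.8–6.4% |
| Kauermann–Carroll, t26 | 4.6–4.9% | 5.4–5.8% |
| Mancl–DeRouen, t26 | 4.0–4.2% | 4.4–4.6% |
| Robust score | 5.0–5.3% | 5.3–5.7% |

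A differently built null model (beta-distributed practice completion probabilities, no hazard before age 11, delayed entry, 3.5 years of follow-up) gave these sizes for Wald z:
- 6.9% at ICC 0.01
- 7.1% at ICC 0.03
- 6.7% with two patient covariates in the model
- 8.4% with size CV 0.6
- 9.6% at 7 per arm

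In that model, t26 alone brought the base case to 5.6%. Adding a variance correction of 28/26, which equals 14/13, brought it to 4.8%.

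**Bootstrap.** This used 12,000 null trials with 500 resamples each, on the arm difference in practice proportions (ICC 0.01, 30% completing). Resampling within arm gave a variance 6.5% too small and a size of 7.1% with a normal reference. Unstratified resampling gave a variance 2.6% too small and 6.5%. Within-arm resampling with k/(k − 1) and t26 gave 5.0%.

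**Power cost.** Taking 85.5% at face value, the standardised effect is 1.058 + 1.960 = 3.018. Moving to the t26 critical value gives Φ(3.018 − 2.056) = 83.2%. If the 85.5% had come from an uncorrected Wald z, the matching noncentrality is 2.964, and the corrected t26 test has 81.4%.

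**The case against.** The strongest reply is that the 7% belongs to an implementation the SAP does not name. Robust covariance covers corrected and uncorrected sandwiches, and Wald and score tests, and the robust score test is close to 5%. The case for Wald rests on the later sections, which describe the primary approach through adjusted standard errors; that is suggestive, not decisive. This stands as a limit on the claim: the plan leaves the test open and does not prescribe a faulty one. It does not remove the problem, since the permitted readings differ by about 2 points and the ordinary one is anti-conservative.

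Other limits also stand:
- The excess is modest with equal practices. The 8.2–8.6% rests on a CV that the SAP does not give.
- The bootstrap figures come from a simpler estimator than the planned Cox-based survival difference, and the normal reference is assumed.
- The stated power comes from a log-rank simulation of 1,000 datasets (Monte Carlo SE √(0.855 × 0.145/1000) = 1.1 points), so the power cost is approximate.
- The SAP promises p-values and does not mention intervals, so the coverage figure applies only if intervals are reported.
- The 7-per-arm case is a power scenario, not a planned analysis. As a statement about ESS, "this reduction in ESS is consistent with (a) an ICC of 0.03; (b) 7 practices per arm (c) 34 patients per practice" is correct. What fails is equivalence for the test: two of the three cases keep 28 practices and the other has 14.

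**Conclusion.** The concern holds, with high confidence, and should be dealt with. In its ordinary form, the primary test has a type I error of about 7% against a declared 5%. Closed form and simulation agree on this for 14 equal practices per arm, and the closed-form result needs only equal sizes and approximate normality of practice-level contributions. Inflation grows with unequal practice sizes (8.2–8.6% at the assumed CV of 0.6) and would be about 9.5% with 7 practices per arm. The result is conditional on an uncorrected Wald z. A robust score test would be near nominal, which is why the form has to be settled in advance. The age-13 bootstrap has the same weakness, at roughly 6.5–7.1% with a normal reference, on the evidence of a simpler estimator.

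**What to change.** State that every test and 95% interval for the practice-level treatment indicator uses a cluster sandwich with the Kauermann–Carroll or Mancl–DeRouen correction, referred to t on the number of practices minus 2 degrees of freedom. The simpler k/(k − 1) factor is enough only if practice sizes are nearly equal. A robust score test or a practice-level permutation test is an acceptable alternative for the p-value. For completion by age 13, resample practices within arm, multiply the bootstrap variance by k/(k − 1) and use the same t reference. Restate power under the chosen test. If the analysis has already been run, report a corrected or permutation p-value beside the original.

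The cost is a few sentences and a few lines of code. Stated power falls by about 2–4 points (85.5% to 83.2% or 81.4%), and part of that loss is only the removal of excess type I error. The exact loss depends on hazard shapes the SAP does not give. Mancl–DeRouen is slightly conservative (4.0–4.6% in these simulations).

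### Completion by age 13 is given two different estimators, and the one in the SAP's main text assumes proportional hazards that its own power assumptions rule out

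*SAP*

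**What the plan says.** Four places in the SAP bear on how completion by 13 is estimated.

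- **Section b (completion by age 13).** The arm-specific curves are "based on the Cox regression models fitted for the primary analysis, using the estimated baseline hazard function", and "the statistic of interest is the difference between these estimates at age 13". Standard errors come from a bootstrap that resamples practices.
- **Summary table at the end.** The method for the same outcome is "KM estimates with cluster bootstrap for variance estimation".
- **Other considerations.** The text gives Kaplan-Meier a supporting role: "We will also perform a sensitivity analysis using Kaplan-Meier curves to assess the validity of some of the assumptions made by the Cox model". It then adds that "comparison of Kaplan-Meier curves at age 13 allows us to obtain more direct estimates of the treatment's effect on this particular endpoint". Proportional hazards will be tested, and "if found to be violated, we will employ alternative modeling strategies (e.g., time-dependent covariates/interactions, additive hazards regression").
- **Section a (power assumptions).** For controls, "we have assumed that the hazard in the control arm is 0 between 9 and 11 years of age"; for the other arm, "the hazard in the treatment arm starts to increase from age 9".

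**The concern.** The text and the table name different main analyses for one outcome, and they are not interchangeable. A Cox model with a treatment indicator gives both arms the same baseline hazard, multiplied by one constant. Its curve at 13 is therefore shaped by timing differences at every other age under observation, before and after 13.

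Hyp 2b asks whether more children are complete by 13, which is a different question from whether they complete earlier. An estimator that mixes the two can report a difference at 13 where there is none, or hide one that exists. If proportional hazards is rejected, the fallback is an open list that does not say what then decides Hyp 2b. At least three estimators could then be reported, with the choice made after the data are seen.

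**Working it through.** **1. Does proportional hazards hold under the plan's own assumptions?** The hazard ratio at age *a* is h1(a)/h0(a). From 9 to 11 the denominator is 0 and the numerator is positive, so the ratio is unbounded. After 11 it is finite. No constant ratio fits. This step needs no outside assumption.

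**2. The plan's power figure (86.4% for 30% v 39%).** Inputs from section a: 14 practices per arm, 100 patients each, ICC 0.01. Effective size per arm = 1400/(1 + 99 × 0.01) = 1400/1.99 = 703.5. A two-sided 5% comparison of two proportions then has 94.5% power, not 86.4%. The SAP's figure comes from a simulation whose hazard shapes and entry ages are not given, so it is neither confirmed nor refuted. In simulations with practice-effect SD 0.10 to 0.18, entry over 9-10 or 9-11, and both hazards flat or both rising, Kaplan-Meier power ran from 73% to 99% and Cox power from 2% to over 99%. One figure cannot describe both estimators.

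**3. How far off can the Cox difference be?** From the SAP: 30% v 39% at 13, control hazard 0 to 11, treated hazard from 9, delayed entry, entry at 9-10 years, follow-up 3.5 years (power section) or 4 years (Overall Strategy). Assumed:

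- control hazard after 11 flat or rising linearly;
- treated hazard rising linearly from 9, or rising to 11 then flat;
- entry all at 9.0 (4 years only, since 9.0 + 3.5 = 12.5 stops short of 13), uniform 9-10, or uniform 9-11;
- children not yet complete at entry, and no covariates.

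That gives 2 × 2 × 5 = 20 settings.

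With Y0 and Y1 the at-risk functions, the large-sample Cox ratio θ solves ∫Y1h1 = ∫[θY1/(Y0+θY1)](Y0h0+Y1h1). The baseline is L0(13) = ∫ from 9 to 13 of (Y0h0+Y1h1)/(Y0+θY1). The reported difference is exp(-L0) - exp(-θL0).

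*Worked case: control rising, treated rising then flat.* The control slope solves 2·s0 = -ln 0.70 = 0.357, so s0 = 0.178. The treated slope solves 6·s1 = -ln 0.61 = 0.494, so s1 = 0.0824 and the hazard is 0.165 per year from 11. The true ratio is unbounded before 11, 0.165/0.089 = 1.85 at 11.5, and 0.165/0.357 = 0.46 at 13. The Cox average depends on which ages are observed (4 years of follow-up; differences taken before rounding):

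| Entry | θ | L0(13) | Control | Treated | Difference (true 9) |
|---|---|---|---|---|---|
| all at 9.0 | 1.559 | 0.338 | 28.6% | 40.9% | +12.3 |
| uniform 9-10 | 1.164 | 0.394 | 32.6% | 36.8% | +4.2 |
| uniform 9-11 | 0.874 | 0.450 | 36.3% | 32.5% | -3.7 |

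*All 20 settings, in percentage points:*

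| Estimator at 13 | True 9 | True 0 (30% in both arms) |
|---|---|---|
| Proportional Cox (section b) | -3.7 to 12.3; off by more than 2 in 12 of 20 | -11.9 to +2.5; off by more than 2 in 9 of 20 |
| Fallback: Cox with arm × linear age | 8.5 to 11.8 | -0.4 to +2.5 |
| Fallback: constant-effect additive hazards | -5.5 to 12.1 | -18.4 to +2.3 |
| Kaplan-Meier by arm, delayed entry | 9.0 | 0 |

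Under one shape pair (control flat from 11, treated rising linearly) the Cox error is small: 8.1 to 10.0, and -0.9 to +0.8. With both hazards flat, outside the 20 settings, Cox gives -0.4 to 12.0 and -8.6 to +2.3. In the last row of the worked case the two fallbacks give 11.4 and -5.5 for the same data.

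**4. Simulation check.** I ran 400 trials per setting with 2 × 14 × 100 children, practice-effect SD 0.18 (ICC about 0.01) and 200 practice-level bootstrap samples within arm. For true 9, the mean Cox difference was -3.9 to 12.5 and the mean Kaplan-Meier difference 8.7 to 9.3, with Kaplan-Meier power 90-96%. For true 0, the means were -11.5 to 2.5 and -0.3 to 0.2. A proportional-hazards test (arm × age score test, ignoring clustering) rejected in about 100% of trials wherever the Cox bias exceeded 2 points, and in 12-100% elsewhere.

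**The case against.** **The prose agrees with itself.** Section b makes Cox the main analysis and Other considerations makes Kaplan-Meier the check, so the conflict could be one table cell, and readers would see both results. This is a fair reading. Correcting the cell towards Cox, however, would keep the estimator that the power assumptions contradict. The remark that the log-rank test stays valid concerns testing equality of curves, not estimating a proportion at 13.

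**The fallback would catch the worst cases.** The proportional-hazards test nearly always rejects where the bias is large, and the first-listed alternative then lands near the truth (8.5 to 11.8). That stands as far as it goes, but additive hazards is listed beside it and can reach -5.5. Hyp 2b would be decided by an estimator the plan does not name.

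**The wrong sign is one corner.** Only one of the 20 settings is negative for true 9, and with entry over 9-10 Cox stays between 4.2 and 11.1. Zero control hazard is a power assumption, and covariates were left out. All of this is true, and it limits the size that can be claimed.

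**The target is a choice.** Children enrolled at 10 or later were not under the intervention from 9. If the target were completion among the children actually enrolled, the true difference would be 5.5 to 9.0 across the 20 settings. With both hazards flat and entry 9-11 it would be +0.8, where Cox gives +0.9 (3.5 years) or -0.4 (4 years). In that case most of the apparent bias is a difference in target. But the SAP itself aims at the age-scale curve at 13 with delayed entry, and with a rising control hazard Cox can miss both targets (-3.7 against 5.5).

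**Kaplan-Meier has costs.** It drops covariate adjustment, and its bootstrap test was not exactly at level. Both points stand and are taken up in the fix.

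**Conclusion.** The concern holds. Two parts rest on the text alone: the SAP names two different main estimators for Hyp 2b, and the one in section b needs a proportionality that section a's assumptions exclude. A third also follows from the text: the non-proportionality branch does not say which estimate decides.

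The size is an illustration that depends on assumed hazard shapes, entry ages and follow-up. The section b estimate can be nearly right, too large, too small or, in one setting of 20, of the wrong sign. The outcome is secondary and the primary test is not affected, so this is a point to correct before analysis and not a threat to the trial's main conclusion.

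**What to change.** - **Section b:** replace the Cox-based curves with an estimator fitted by arm at age 13 that does not impose proportional hazards between arms. Use Kaplan-Meier, as the table already says, or Cox stratified by arm with curves averaged over the pooled covariates if adjustment is to be kept. State delayed entry and a practice-level bootstrap within arm.
- **Deciding rule:** say that this estimator decides Hyp 2b whatever the proportional-hazards test shows, and make the proportional Cox version a sensitivity analysis.
- **Other considerations and summary table:** bring both into line with section b.
- **Power:** state which estimator the 86.4% refers to.

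The cost is one paragraph and a few sentences, with no new data. Variance rises somewhat: in the 20 settings the SD was 2.3-2.9 points for Kaplan-Meier against 2.0-2.7 for Cox (ratio 1.00-1.23). It reached 3.4 against 2.3 when the treated hazard was already high at 9.0 and early risk sets were small. With 14 practices per arm and a normal critical value, the Kaplan-Meier bootstrap test rejected in 4-10% of trials with no true difference, so the plan should also state how it allows for the small number of practices.
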